9.5 NOTIFICATION OF DEATHS

Only deaths that are assessed to be caused by the IMP will be reported to the sponsor. This report will be immediate using safety report form.

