9 PHARMACOVIGILANCE

9.1 DEFINITIONS

Term	Definition
Adverse Event (AE)	Any untoward medical occurrence in a participant to whom a medicinal product has been administered, including occurrences which are not necessarily caused by or related to that product.
Adverse Reaction (AR)	
An untoward and unintended response in a participant to an investigational medicinal product which is related to any dose administered to that participant.
 
The phrase "response to an investigational medicinal product" means that a causal relationship between a trial medication and an AE is at least a reasonable possibility, i.e., the relationship cannot be ruled out.
 
All cases judged by either the reporting medically qualified professional or the Sponsor as having a reasonable suspected causal relationship to the trial medication qualify as adverse reactions. It is important to note that this is entirely separate to the known side effects listed in the SmPC. It is specifically a temporal relationship between taking the drug, the half-life, and the time of the event or any valid alternative etiology that would explain the event.

Serious Adverse Event (SAE)	
A serious adverse event is any untoward medical occurrence that:
 
 results in death is life-threatening requires inpatient hospitalisation or prolongation of existing hospitalisation results in persistent or significant disability/incapacity consists of a congenital anomaly or birth defect 
Other 'important medical events' may also be considered serious if they jeopardise the participant or require an intervention to prevent one of the above consequences.
 
NOTE: The term "life-threatening" in the definition of "serious" refers to an event in which the participant was at risk of death at the time of the event; it does not refer to an event which hypothetically might have caused death if it were more severe.

EudraCT number: 2021-000071-36

SHORT TITLE: DORA

Serious Adverse Reaction (SAR)
	
An adverse event that is both serious and, in the opinion of the reporting Investigator, believed with reasonable probability to be due to one of the trial treatments, based on the information provided.

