9.3 RECORDING AND REPORTING OF SAEs, SARs AND SUSARs

Safety monitoring will be performed during the trial visits and end at 24 hours post last study dose ingestion (i.e., end of the participation) due to short half-live of aspirin and fast elimination.

Long term follow up will not be performed as teratogenicity of a single low dose of aspirin is not recognized.

Safety reporting form will be completed by a member of the research team, assessed by PI/CI and reported to the Sponsor’s team

Where a participant withdraws consent safety assessments will be performed at 24 hours post aspirin ingested at the research visit.

EudraCT number: 2021-000071-36

SHORT TITLE: DORA

All SAEs occurring from the time start of trial treatment until 24 hours post cessation of trial treatment must be recorded on the safety assessment form and e-mailed to the Sponsor within 24 hours of the research staff becoming aware of the event. Once all resulting queries have been resolved, the Sponsor will request the original form should also be posted to the Sponsor and a copy to be retained on site.

For each SAEs the following information will be collected:

- full details in medical terms and case description
- event duration (start and end dates, if applicable)
- action taken
- outcome
- seriousness criteria
- causality (i.e. relatedness to trial drug / investigation), in the opinion of the investigator
- whether the event would be considered anticipated

Any change of condition or other follow-up information should be e-mailed to the Sponsor as soon as it is available or at least within 24 hours of the information becoming available. Events will be followed up until the event has resolved or a final outcome has been reached.”

All SAEs assigned by the CI/PI or delegate as both suspected to be related to IMP-treatment and unexpected will be classified as SUSARs and will be subject to expedited reporting to the Medicines and Healthcare Products Regulatory Agency (MHRA). The sponsor will inform the MHRA, the REC and Marketing Authorisation Holder of SUSARs within the required expedited reporting timescales.

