9.4 RESPONSIBILITIES

Principal Investigator (PI):

Checking for AEs and ARs when participants attend for treatment / follow-up.

Using medical judgement in assigning seriousness, causality and whether the event/reaction was anticipated using the SmPC.

Ensuring that all SAEs are recorded and reported to the sponsor within 24 hours of becoming aware of the event and provide further follow-up information as soon as available. Ensuring that SAEs are chased with Sponsor if a record of receipt is not received within 2 working days of initial reporting.

Ensuring that AEs and ARs are recorded and reported to the sponsor in line with the requirements of the protocol.

Chief Investigator (CI) / delegate or independent clinical reviewer:

EudraCT number: 2021-00071-36

SHORT TITLE: DORA

Clinical oversight of the safety of patients participating in the trial, including an ongoing review of the risk / benefit.

Using medical judgement in assigning the SAEs seriousness, causality and whether the event was anticipated (in line with the SmPC) where it has not been possible to obtain local medical assessment.

Immediate review of all SUSARs.

Review of specific SAEs and SARs in accordance with the trial risk assessment and protocol as detailed in the Trial Monitoring Plan.

Assigning Medical Dictionary for Regulatory Activities (MedDRA) or Body System coding to all SAEs and SARs.

Preparing the clinical sections and final sign off of the Development Safety Update Report (DSUR).

Sponsor:

Central data collection and verification of AEs, ARs, SAEs, SARs and SUSARs according to the trial protocol onto a database.

Reporting safety information to the CI, delegate or independent clinical reviewer for the ongoing assessment of the risk / benefit according to the Trial Monitoring Plan.

Reporting safety information to the independent oversight committees identified for the trial (Data Monitoring Committee (DMC) and / or Trial Steering Committee (TSC)) according to the Trial Monitoring Plan.

Expedited reporting of SUSARs to the Competent Authority (MHRA in UK) and REC within required timelines.

Notifying Investigators of SUSARs that occur within the trial.

Checking for (annually) and notifying PIs of updates to the Reference Safety Information for the trial.

Preparing standard tables and other relevant information for the DSUR in collaboration with the CI and ensuring timely submission to the MHRA and REC.

Trial Management Group (TMG)

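### Section 9.5 limits death reports to the sponsor to those judged IMP-caused, contradicting the all-SAE rule in sections 9.1, 9.3 and 9.4

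*Protocol*

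**What the plan says.** Four parts of Protocol section 9 bear on how a death is reported.

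- **9.1 Definitions.** An adverse event covers untoward occurrences after a medicinal product is given, "including occurrences which are not necessarily caused by or related to that product". An SAE is any such occurrence meeting a seriousness criterion, the first of which is that it "results in death". Neither definition requires a causal link.
- **9.3 Recording and reporting.** "All SAEs occurring from the time start of trial treatment until 24 hours post cessation of trial treatment must be recorded" and "e-mailed to the Sponsor within 24 hours of the research staff becoming aware of the event". Causality is one of the items collected for each SAE.
- **9.4 Responsibilities.** The PI's duties include "Ensuring that all SAEs are recorded and reported to the sponsor within 24 hours of becoming aware of the event". The sponsor collects and verifies safety events centrally and prepares the standard tables for the DSUR.
- **9.5 Notification of deaths.** "Only deaths that are assessed to be caused by the IMP will be reported to the sponsor". The next sentence adds: "This report will be immediate using safety report form".

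The only reporting exemption in section 9.2 is for pre-existing conditions. The section on roles and responsibilities records the decision not to convene a DMC. The last paragraph of section 9 before 9.5 has the TMG act as TSC and review safety data.

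**The concern.** Section 9.5 makes a site-side causality judgement the condition for telling the sponsor about a death. Elsewhere in section 9, causality is recorded about an event that is reported in any case. The result is an odd ordering: an unrelated, non-fatal hospital admission during the reporting period goes to the sponsor within 24 hours, while an unrelated death in the same period, on the words of 9.5, does not.

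What is at stake is the completeness of the safety record. If 9.5 were followed, a death judged unrelated could be absent from the sponsor's database and from the DSUR tables built on it. The sponsor would then have no occasion to query the causality assessment. Section 9.5 is the section named for deaths, so it is where staff would naturally look if one occurred.

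**Working it through.** No arithmetic underlies the contradiction, and the plan gives no figure to reproduce. The check is to take each kind of event and ask what each section requires.

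**Reporting window.** Section 9.3 runs from the start of trial treatment to 24 hours after it stops, and says that safety monitoring ends 24 hours after the last study dose. Section 8.6 places the two doses one week apart. Taking the second dose as the end of treatment, the window is 7 days + 1 day = about 8 days per woman. With at most 18 women, all completing, that is 18 × 8 = 144 participant-days.

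| Event | 9.3 | 9.4 (PI duty) | 9.5 | Compatible? |
|---|---|---|---|---|
| Death in window, judged IMP-caused | Report within 24 h | Report within 24 h | Report immediately | Yes; an immediate report also meets 24 h |
| Death in window, judged not IMP-caused | Report within 24 h | Report within 24 h | Not reported | **No** |
| Death after window, judged IMP-caused | Silent | Report, as no window is stated | Report immediately | Yes |
| Death after window, judged not IMP-caused | Silent | Report, if read without a window | Not reported | Depends on whether 9.4 inherits the 9.3 window |
| Non-fatal SAE in window, judged unrelated | Report within 24 h | Report within 24 h | Does not apply | Yes |

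The second row is a direct conflict. Three ways of reconciling the text were tried.

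1. *Section 9.5 only adds a faster route for IMP-caused deaths.* The sentence begins with the word *only* and settles whether a death is reported at all. Speed is dealt with in a separate sentence.
2. *Section 9.5 concerns only deaths after the SAE window.* It states no time limit in either direction.
3. *Another section removes deaths from the SAE rule or ranks the rules.* None does in the text available. The exemption in 9.2 for pre-existing conditions does not cover unrelated deaths in general.

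The contradiction therefore stands on the wording.

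**The case against.** The strongest defence is that two explicit instructions, in 9.3 and 9.4, already require every SAE to be reported, and that 9.2 has all serious events recorded and assessed by the PI or CI. Staff might well follow those and report the death. Appendix 3, the safety reporting flow chart, is not visible in the copy reviewed and may show how deaths are routed. This limits what can be said about what staff would do. It does not remove the conflict, because nothing in the visible text says that 9.3 prevails over 9.5.

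A reader might also infer several stronger points that the protocol does not support.

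- *Sponsor review is the only check on the site's causality call.* It is not. Section 9.4 gives clinical oversight to the CI, a delegate or an independent clinical reviewer. The TMG acts as TSC and includes a sponsor representative. However, the CI/PI sits on the TMG, so it is not independent. The independent reviewer is named only as an alternative to the CI, and no section says that a death withheld under 9.5 would reach that person.
- *Deaths have the weakest reporting rule in the protocol.* For deaths judged IMP-caused, 9.5 is stricter than 9.3 and 9.4, since it asks for an immediate report and sets no window. The weakness is confined to deaths judged unrelated.
- *The protocol gives the sponsor a clear right to judge causality, which 9.5 defeats.* The adverse reaction definition in 9.1 does allow either the reporting professional or the sponsor to make that judgement. The serious adverse reaction definition, though, rests on the reporting investigator's opinion, and 9.3 gives SUSAR classification to the CI, PI or delegate. The sponsor's role for a fatal event is thus less settled than that argument needs.

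**Conclusion.** The contradiction is real. A death between the start of treatment and 24 hours after its cessation, judged not caused by the IMP, must reach the sponsor under 9.3 and 9.4 and is excluded by 9.5. If 9.5 were followed, that death could be missing from sponsor safety data in a trial without a DMC.

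The expected numerical effect is close to nil. At most 18 women are followed for about 8 days each, and the sponsor itself rates the mortality risk as low. The documents give no death rate for this setting, so no probability is attached. No endpoint, power figure or planned analysis changes. The case for correction is that a rule on deaths matters only when one occurs, and as written it cannot then be followed consistently.

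Two assumptions apply: that the second dose marks the end of treatment for the 9.3 window, and that Appendix 3 does not already settle the routing. Even if it did, the sentence in 9.5 would still need correcting.

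**What to change.** Remove the causality filter from 9.5 and reconcile it with 9.1, 9.3 and 9.4. Suggested wording:

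*Every death occurring in the SAE reporting period defined in section 9.3, whatever its cause, is an SAE and is sent to the sponsor within 24 hours of the research staff becoming aware of it. Causality is recorded as a separate item and does not determine whether the death is reported. A death assessed as caused by the IMP is reported immediately, whenever it occurs.*

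The last sentence matters. Pointing 9.5 to 9.3 alone would lose two protections already in place: the immediate report and the absence of a time window for IMP-caused deaths.

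While amending, state whether the PI duty in 9.4 is meant to share the 9.3 window, and check that the Appendix 3 flow chart agrees.

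The cost is a short protocol amendment, handled under section 13.10. The causality item is already collected for each SAE under 9.3, so no new data item or procedure is needed and almost no extra work is expected.

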9.6 OVERDOSE

No overdose expected over duration of this trial as participants will be observed taking their aspirin and will be asked to abstain from taking aspirin during the washout period.

In an unlikely event of an overdose please refer to SmPC.

9.7 REPORTING URGENT SAFETY MEASURES

If any urgent safety measures are taken the CI/Sponsor shall immediately and in any event no later than 3 days from the date the measures are taken, give written notice to the MHRA and the relevant REC of the measures taken and the circumstances giving rise to those measures.

9.8 THE TYPE AND DURATION OF THE FOLLOW-UP OF PARTICIPANTS AFTER ADVERSE REACTIONS.

Bedside observations will be performed for a duration of 4 hours post IMP ingestion.

Self-reported wellbeing check will be conducted at 20 hours post IMP ingestion.

In case of any (S)ARs, follow up care will be given until resolution.

For the duration of participation in the trial, any SUSAR will need to be reported to the Sponsor irrespective of how long after IMP administration the reaction has occurred until resolved.

9.9 DEVELOPMENT SAFETY UPDATE REPORTS

The Development Safety Update Report (DSUR) must be submitted to MHRA on an annual basis. A copy will also be provided to REC. The DSUR will be submitted within 60 days of the Developmental International Birth Date (DIBD) of the trial.

It is the responsibility of the CI to complete, review and submit the DSURs.

SHORT TITLE: DORA

EudraCT number: 2021-000071-36

10 STATISTICS AND DATA ANALYSIS

10.1 SAMPLE SIZE CALCULATION

With a sample of 14 participants (7 participants in each group), we would have 80% power to detect a 1 SD difference in the area under the serum Tbx concentration curve (AUC) between two doses of aspirin. This is based on an Equivalence Test for Treatment Means in 2 x 2 Crossover Designs test with a common standard deviation of 109.7 (based on serum Tbx AUC data from healthy female volunteer study taking either 75mg or 150mg of aspirin) and alpha level of 0.05.

In this sample size calculation we have used common within the population SD as within-subject SD was not available. Considering that within-subject SD tends to be lower than between-subject SD, we will be able to achieve > 80% power.

After allowing for a 25 % dropout following study entry, we expect to recruit up to 18 participants to reach a sample size of 14 full data sets.

Sample size calculation was performed under supervision of [name], a Statistical Consultant, School of Mathematics, Statistics & Physics, Newcastle University.

10.2 PLANNED RECRUITMENT RATE

For the sample size of 14 participants we are planning to recruit up to 18 participants to account for potential withdrawals (25%). We anticipate a recruitment rate of 3 participants per month and thus expect to finish recruitment in 5-6 months with additional 2 months to complete laboratory assays and data analysis.

10.3 STATISTICAL ANALYSIS PLAN

Descriptive statistics will be used to describe the study population, Tbx2 and SA levels. Analyte levels in the 75 mg and 150 mg group will be compared at each time point by independent t-test or by nonparametric Wilcoxon tests depending of the nature of the data obtained. The area under the curve (AUC) for all analyses over the 24 hour period will also be analyzed using analysis of variance including sequence, period, and treatment effects. IBM SPSS version 21 statistical software will be used to analyse the data.

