4 TRIAL DESIGN

Cross-over 2 x 2 design comparing PK/PD of a single oral dose of 75 mg aspirin with those of 150 mg of aspirin in pregnant women. Each of the participants will be given all the trial treatments in successive periods. The order in which the participants receive each treatment is determined at random.

The study aims to compare the plasma concentrations of SA and the pharmacological effects (by measuring serum Tbx concentration) of two doses of aspirin prescribed in clinical practice; it is not designed to compare the efficacy or safety of the medicine

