7.3 THE RANDOMISATION SCHEME

7.3.1 METHOD OF IMPLEMENTING THE RANDOMISATION/ALLOCATION SEQUENCE

All participants will be randomised to a sequence of 75 mg – washout – 150 mg or 150mg-washout-75 mg treatment. Sealed Envelope, an online software application, will be used for 1:1 randomization. The randomisation process will be administered by a member of the research team.

SHORT TITLE: DORA

EudraCT number: 2021-000071-36

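### Section 10.3 prescribes an independent t-test at each time point, although every woman takes both doses and the values are paired

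*Protocol*

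**What the plan says.** Protocol section 4 describes the crossover: "Each of the participants will be given all the trial treatments in successive periods". Section 7.3.1 fixes the two orders: "All participants will be randomised to a sequence of 75 mg – washout – 150 mg or 150mg-washout-75 mg treatment". Section 8.6 confirms that each woman takes one tablet on one occasion and two on the other.

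Section 10.3 then treats the two doses as groups at the level of single time points. Analyte levels "will be compared at each time point by independent t-test or by nonparametric Wilcoxon tests", the choice depending on the nature of the data. The same section analyses the AUC separately, by "analysis of variance including sequence, period, and treatment effects".

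Section 10.1 sizes the trial with a procedure for 2 x 2 crossover designs: "With a sample of 14 participants (7 participants in each group), we would have 80% power to detect a 1 SD difference". It uses a "common standard deviation of 109.7" taken from the population because no within-subject SD was to hand. It expects more than 80% power because the within-subject SD tends to be the smaller one.

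**The concern.** An independent t-test assumes that the 75 mg values and the 150 mg values come from unrelated people. Here no such groups exist: 14 women supply 28 values in 14 pairs. The test leaves all between-woman variation in its error term, which is the variation a crossover is chosen to remove, and it makes no allowance for period.

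The stake is precision. If a woman's two values are positively correlated, confidence intervals for the dose difference at each time point come out too wide, p-values are too large, and a real difference can be missed in a trial of only 14 women. The choice also conflicts with section 10.1, whose expected gain in power appears only if the analysis works within women.

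This is a named test that does not fit the design, not a detail left open. A separate analysis plan that used a paired test would contradict the protocol.

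**Working it through.** **Inputs from the protocol.** n = 14 women, 7 per sequence; difference of interest 1 SD; alpha 0.05; SD 109.7 for thromboxane AUC (all section 10.1). The 1 SD was set for the AUC. It is borrowed here for the time-point comparisons because the protocol gives no other effect size.

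**Assumption.** The within-woman correlation rho is not given. The range shown is 0 to 0.7, with equal variance under both doses and no period effect.

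**Step 1: the plan's own figure.** Taking 109.7 as the within-subject SD, the standard error of the dose difference is SD x sqrt(2/14) = 0.378 SD. The noncentrality is 1/0.378 = 2.65 on 14 - 2 = 12 degrees of freedom. A one-sided 0.05 test then has 80.2% power, which matches the stated 80%. A two-sided test has 68.1%. The equivalence test that section 10.1 names has 60.4% (margin 1 SD, true difference 0, 0.05 per side). That mismatch is a separate matter. What counts here is that the 80% comes from a within-participant crossover calculation.

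**Step 2: standard errors.** With total SD s:
- true SE of the difference in means = s x sqrt(2(1 - rho)/14)
- SE that the independent t-test estimates = s x sqrt(2/14) = 0.378 s, whatever rho is
- ratio = 1/sqrt(1 - rho)

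**Step 3: type I error and power, two-sided 0.05.** These were simulated for 14 pairs from a bivariate normal distribution, with 26 degrees of freedom for the independent test and 13 for the paired test.

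| rho (assumed) | True SE (in s) | Independent SE (in s) | Ratio | Type I error, independent | Power 1 SD: independent / paired | Power 0.5 SD: independent / paired |
|---|---|---|---|---|---|---|
| 0 | 0.378 | 0.378 | 1.00 | 5% | 72% / 69% | 25% / 23% |
| 0.3 | 0.316 | 0.378 | 1.20 | about 2% | 75% / 83% | 21% / 31% |
| 0.5 | 0.267 | 0.378 | 1.41 | about 0.8% | 79% / 93% | 18% / 41% |
| 0.7 | 0.207 | 0.378 | 1.83 | about 0.1% | 83% / 99% | 14% / 61% |

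The paired test keeps its 5% throughout. The loss of power is 8, 14 and 16 points at 1 SD and 10, 23 and 47 points at 0.5 SD, for rho 0.3, 0.5 and 0.7.

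**Step 4: is rho likely to be above zero?** Section 10.1 presumes so. With within-subject SD = s x sqrt(1 - rho), a within-subject SD below the population SD means rho > 0.

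**Step 5: the AUC model, only if fitted with exactly the three listed terms.** Power for 1 SD would be 75%, 78% and 83%, against 83%, 93% and 99% with participant in the model. In AUC units the standard error would be 109.7 x 0.378 = 41.5, against 34.7, 29.3 and 22.7.

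**The case against.** Five points can fairly be made for the plan.

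- **The AUC analysis.** A reader might infer that the primary analysis is wrong too, since no participant term is named. The protocol does not support that. Sequence, period and treatment are the fixed effects of the standard crossover analysis of variance, with participant within sequence as its usual error stratum. The list is introduced as what the analysis includes, not as everything in it, and the error term is the kind of detail commonly left to a statistical analysis plan. This point stands: the AUC part is a clarification, not a demonstrated error.
- **Endpoints.** The primary endpoint is AUC (section 3.3) and the secondary is time for salicylic acid to reach baseline (section 3.4). The time-point comparisons are neither. This stands and limits the consequences.
- **The Wilcoxon test.** The name covers the paired signed-rank test, which would suit, and the rank-sum test, which would not. Its place beside an independent t-test suggests the latter, but the text does not settle it.
- **Direction.** A reader might infer a risk of false-positive dose differences. There is none from this source: the type I error falls below 5%.
- **Size.** It rests on an assumed correlation, and at 1 SD the loss is moderate. This stands. At zero correlation the independent test even has slightly more power (72% against 69%), through its extra degrees of freedom.

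None of this rescues the independent t-test itself, which assumes a structure that the design does not have.

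**Conclusion.** The point holds for the time-point comparisons: section 10.3 names an independent t-test for paired data, which is wrong as written. With 14 women, standard errors are too large by a factor of 1.20 to 1.83 and power for 1 SD is 8 to 16 points too low over assumed correlations of 0.3 to 0.7, with larger losses for 0.5 SD. These sizes assume positive correlation, equal variances and roughly normal data. The protocol does not give the correlation, but its own sample size argument relies on a smaller within-subject SD.

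The point does not extend to a finding that the primary AUC analysis ignores pairing. That would follow only if the model were fitted with the three listed terms and nothing else, which the text does not say.

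**What to change.** In section 10.3, replace the independent t-test with a within-participant analysis. The preferred form at each time point is a crossover model with dose, period and sequence as fixed effects and participant as a random effect, which also handles period. A paired t-test is a simpler option, with the stated limitation that it ignores period.

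State that the Wilcoxon test is the signed-rank test on within-participant differences.

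As a clarification, add that the AUC analysis of variance includes participant within sequence.

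The cost is a change of wording before the data are analysed. No extra participants, samples or visits are needed, and SPSS, the software already named, fits these models.

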3.3 PRIMARY ENDPOINT/OUTCOME

Area under the serum Tbx concentration versus time curve (AUC_{Tbx}) and SA plasma concentration versus time curve (AUC_{SA}).

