3.5 TABLE OF ENDPOINTS/OUTCOMES

Objectives	Outcome Measures	Time points of evaluation of this outcome measure (if applicable)

Primary Objective
 
To compare aspirin pharmacokinetics (plasma SA concentrations) and pharmacodynamics (serum TbxB2 concentrations) in pregnant women at 11-16 weeks gestation' following the administration of a single oral dose of either 75 mg or 150 mg aspirin.
	
AUC for serum TbxB2 and plasma SA concentration in participants taking 75 mg and 150 mg of aspirin
	
Blood sampling on two occasions in accordance with 2 x 2 crossover design:
 
Pre medicated, 1, 2, 3, 4, 15, 16, 17, 18, 19 hours post medication

Secondary Objectives
 
Time to baseline SA
	
SA concentration
	
Derived from the samples above

SHORT TITLE: DORA

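### Section 10.3 lets the obtained data choose between an independent t-test and a Wilcoxon test for the time-point comparisons, with no criterion; one within-woman log-scale analysis should be fixed in advance

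*Protocol*

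**What the plan says.** Protocol section 10.3 plans two kinds of comparison.

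- **Time points.** "Analyte levels in the 75 mg and 150 mg group will be compared at each time point", using "independent t-test or by nonparametric Wilcoxon tests depending of the nature of the data obtained". The section does not say what feature of the data decides, whether the decision is made once or at every time, or whether Wilcoxon means rank-sum or signed-rank. It mentions no transformation.
- **AUC.** This goes to "analysis of variance including sequence, period, and treatment effects", with no choice left to the data.

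Section 3.3 makes AUC the primary endpoint for both analytes ("Area under the serum Tbx concentration versus time curve", and the matching curve for SA). Section 3.4 names one secondary endpoint, the time for SA to return to baseline. The time-point comparisons are neither. The sampling times in section 3.5 are "Pre medicated, 1, 2, 3, 4, 15, 16, 17, 18, 19 hours post medication". Section 4 makes the data paired: "Each of the participants will be given all the trial treatments in successive periods". The planned sample is 14 (section 10.1).

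**The concern.** A rule that picks the test from the observed data has to rest on some check of distribution, and 14 values give such a check little to work with. Two neighbouring times with the same underlying distribution could then get different tests by chance. One test compares arithmetic means and the other compares ranks, so the time course would have no common effect measure. If Wilcoxon means signed-rank, the rule would also switch between an unpaired and a paired comparison.

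What is at stake is how well the time course can be read. That matters here because section 2 ties the value of SA as an adherence test to its level at particular late times, up to 19 hours. An estimated dose ratio with an interval at each time would serve that purpose better than a series of p-values from different tests.

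**Working it through.** **The plan's own figure.** The protocol gives no power for the time-point tests. Its only power figure is for Tbx AUC (section 10.1): "With a sample of 14 participants (7 participants in each group), we would have 80% power to detect a 1 SD difference". With SE = SD × √(2/14), the noncentrality for a 1 SD difference is 1/√(2/14) = 2.65. On 12 df a one-sided 5% test then gives 80.2%. The figure reproduces on that reading, but it concerns AUC and is not used below.

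**Inputs from the protocol.** n = 14; each woman takes both doses; 10 sampling times × 2 analytes = 20 comparisons.

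**Inputs assumed.** Log-normal concentrations, the CVs, the dose ratios, and Shapiro-Wilk at 5% as the check. The protocol gives no distribution for either analyte and names no check.

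**Step 1: how reliable is the check?** Let p be the chance that 14 log-normal values are flagged as non-normal. The chance that at least one of two doses is flagged is 1 − (1 − p)², treating the doses as independent.

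| CV | p | Either dose flagged |
|---|---|---|
| 0.2 | 10% | 19% |
| 0.3 | 17% | 31% |
| 0.4 | 25% | 43% |
| 0.6 | 43% | 67% |
| 0.8 | 58% | 82% |
| 1.0 | 68% | 90% |

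All these data are skewed, so a dependable check would flag nearly all of them.

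**Step 2: would one profile mix tests?** Suppose the choice is made per time point and q is the chance that either dose is flagged. With independent times, the chance that all 10 get the same test is q¹⁰ + (1 − q)¹⁰. At CV 0.3 this is 0.31¹⁰ + 0.69¹⁰ ≈ 0.025, so the profile is mixed in about 97% of trials. Simulation with serial correlation from 0.9 down to 0 gives a mixed profile in 85-97% (CV 0.3), 93-99% (CV 0.5) and 69-88% (CV 0.8) of trials.

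**Step 3: power.** Simulated two-sided 5% tests, n = 14, in percent. The choice is between t and rank-sum for independent tests, and between t and signed-rank for paired tests.

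| Between/within CV, ratio | Choice, independent | Fixed log t, independent | Choice, paired | Fixed log t, paired |
|---|---|---|---|---|
| 0.3/0.2, 1.25 | 30 | 30 | 76 | 78 |
| 0.4/0.3, 1.5 | 61 | 62 | 88 | 92 |
| 0.6/0.4, 1.5 | 25 | 25 | 63 | 72 |
| 1.0/0.6, 2.0 | 35 | 38 | 75 | 86 |

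- Loss from the choice, independent tests: 0, 1, 0 and 3 points.
- Loss from the choice, paired tests: 2, 4, 9 and 11 points.
- Gap between the first and last columns: 48, 31, 47 and 51 points. Nearly all of it comes from pairing.

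A second set of assumptions (log-SD 0.5 or 0.8, within-woman correlation 0.5) gives the same pattern. Choice against fixed log t is 74 v 78, 35 v 42 and 65 v 74 when paired, and 54.6 v 55.5, 17.9 v 18.6 and 42.7 v 45.9 when independent.

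**Step 4: data normal on the raw scale.** Paired choice against paired log t is 68 v 66, 68 v 63 and 87 v 84. The paired choice matches the fixed paired raw-scale t-test (67.8 v 67.7, 68.4 v 68.5, 86.9 v 87.0), so the choice costs nothing and the log analysis is 2-5 points worse.

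**Step 5: type I error.** The paired rule rejects in 4.4-5.0% of null trials in the CV scenarios. The independent rule rejects in about 0.2-0.4%, because it ignores pairing. Taking the smaller of the two paired p-values gives about 5.5-6% in the log-SD scenarios.

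**The case against.** The strongest reply is that no stated endpoint depends on this rule. That is correct, and it limits the point to supporting comparisons. A reader might infer that the primary result is at risk; it is not, because AUC has a fixed model.

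A reader might also infer a general loss of power. The documents do not support that. Every distributional input is assumed, the 2-11 point loss needs skewed data and tests that are already paired, and under the independent tests as written the loss is 0-3 points. Nor is the t-test always the weaker choice when skewness goes undetected. In the log-SD scenarios, among samples not flagged, the independent t-test had more power than rank-sum (61.0 v 51.4%, 32.5 v 23.4%, 63.3 v 48.8%).

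A third tempting reading is that an unblinded team could pick the favourable test. Section 7.4 leaves clinicians, participants and the delivery team unblinded but is silent on the analyst. Sections 11.2 and 13.7 send anonymised data to the university for analysis. Even taking the smaller p-value moves the error rate only to about 5.5-6%.

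The wording also permits one choice for the whole profile, in which case tests would not be mixed along it.

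Finally, a selection criterion is often left to the SAP. That does not fully answer the point: section 10.3 states the data-dependent rule itself, so an SAP would have to follow it or override it.

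**Conclusion.** The point stands in a limited form. For the supporting time-point comparisons, section 10.3 lets the data select the test without a criterion, and at n = 14 that selection is unreliable. A mixed profile is likely (69-99% across the CVs of 0.3 to 0.8 examined) only if the choice is made at each time. The choice does not inflate type I error. Its power cost is about 2-11 points with paired tests, about 0-3 points with the independent tests as written, and nothing if data are normal on the raw scale. These figures rest on log-normality, the CVs shown and Shapiro-Wilk as the check, none of which is in the protocol.

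The larger fault in the same sentence is the independent t-test on paired crossover data. Most of the gain from the change below comes from correcting that, and it should not be credited to removing the choice of test. The change is worth making because it is cheap and gives one interpretable measure throughout; the primary analysis does not depend on it.

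**What to change.** In section 10.3, delete the clause that makes the test depend on the data obtained, and replace the time-point sentence with one pre-stated analysis for both analytes. Suggested wording: *At each post-dose time, log concentration will be analysed with a within-woman crossover model including sequence, period and treatment, as for AUC, and reported as the 150/75 mg geometric mean ratio with 95% confidence interval. A Wilcoxon signed-rank test will be a sensitivity analysis.* This covers 9 post-dose times × 2 analytes = 18 comparisons. Make it together with the correction of the independent test, since one sentence carries both.

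The cost is wording, plus two small downsides:

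- Taking logs needs one fixed rule for values below the assay limit. Its influence should be checked at 15-19 hours, which are 5 of the 9 post-dose times and where SA may be near baseline.
- If the data prove normal on the raw scale, the log analysis gives up about 2-5 points of power.
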